4.3.2 Storage

Pemigatinib drug product should be stored as detailed on the investigational product labeling.

4.3.3 Instruction to Subjects for Handling Study Drug (Pemigatinib)

The subject must be instructed in the handling of study drug as follows:

- To store the study drug at room temperature.
- To only remove from the study drug bottle the number of tablets needed at the time of administration.
- Not to remove doses in advance of the next scheduled administration.
- To make every effort to take doses on schedule.
- To report any missed doses.
- To take study drug immediately upon rising or after a 2-hour fast with a glass of water; the subject should refrain from eating 1 hour after taking study drug.
- If the subject vomits after taking study drug, the subject should not take another dose.
- To keep study drug in a safe place and out of reach of children.
- To bring all used and unused study drug bottles to the site at each visit.

- If a dose of Pemigatinib is missed by more than 4 hours, that dose should be skipped and the next scheduled dose should be administered at the usual time.

4.3.4 Treatment Compliance

Compliance with all study-related treatments should be emphasized to the subject by the site personnel, and appropriate steps should be taken to optimize compliance during the study.

Compliance with Pemigatinib will be calculated by the sponsor based on the drug accountability documented by the site staff and monitored by the sponsor/designee (tablet counts). Subjects will be instructed to bring all study drugs with them to the study visits in order for site personnel to conduct tablet counts to assess study drug accountability. The drug accountability documentation will be used by the sponsor to calculate treatment compliance.

4.3.5 Adverse Events

The most common treatment-emergent adverse events in more than 20% of the patients receiving continuous dose Pemigatinib monotherapy for advanced malignancies were hyperphosphataemia (70%), stomatitis (48%), diarrhea (39%), hair loss (38%), dry mouth (37%), dysgeusia (36%), fatigue (29%), constipation (33%), decreased appetite (27%), nausea (26%), dry eyes (22%), anaemia (21%), asthenia (21%) and palmar-plantar erythrodysaesthesia syndrome (21%) (21).

Hyperphosphatemia can lead to symptoms such as muscle cramps and contractions, numbness or tingling in the mouth. A hyperphosphatemia can be managed with diet modification, phosphate binding drugs or dose modification.

Other common adverse events observed in 10-20% of the patients were abdominal pain, vomiting, back pain, epistaxis, dry skin, increased blood creatinine level, joint pain, decrease of weight, oedema, nail problems, hypercalcaemia, urinary tract infection, pain in extremity and low sodium blood levels (21).

Less common adverse events observed in less than 10% of the patients are pyrexia, dehydration and hypophosphatemia.

Ophthalmic exams are done at baseline and at least once every 12 weeks during treatment. Additional assessments will be done in participants with reported changes in vision.

4.3.6 Treatment Interruptions and Adjustments

Dose interruptions and modifications may occur for individual study subjects. The occurrence of toxicities (related or unrelated to study drug) will guide decisions for treatment interruptions and discontinuation for individual subjects. Treatment with Pemigatinib may be interrupted up to 14 days to allow for resolution of toxicity. Subjects may resume treatment if no medical condition or other circumstance exists that, in the opinion of the investigator, would make the subject unsuitable for further participation in the study. The treating investigator should contact a representative of the sponsor to discuss the case of any subject whose treatment has been delayed for more than 14 days before restarting treatment with Pemigatinib.

Because subjects may enter the study with extensive pretreatment toxicities, these dose reduction rules are provided as guidelines. Individual decisions regarding dose reduction should be made

using clinical judgment and in consultation with the sponsor's medical monitor, taking into account relatedness of the AE to the study drug and the subject's underlying condition. Adverse events that have a clear alternative explanation or transient (\leq 72 hours) abnormal laboratory values without associated clinically significant signs or symptoms may be exempt from dose-reduction rules. In case of occurrence of toxicities the investigator should, if needed, treat/follow up the patient until the toxicity has been resolved.

In cases where study drug should be restarted at a next lower dose, the new dose can be 9 mg on a continuous schedule, and then 6.5 mg, since these were dose cohorts in the INCB 54828-101 study. However, individual decisions regarding dose reduction and new dose level should be made using clinical judgment, utilizing the tablet doses available (4.5 mg and 2 mg) and in consultation with the representative of the study sponsor.

Table. Guidelines for Interruption and Restarting of study drug:

ADVERSE EVENT	ACTION TAKEN
Chemistry	
Step 1: interrupt study drug up to 2 weeks (14 days) until the toxicity has resolved to \leq Grade 1 except by approval of the medical monitor
 
Step 2: If assessed as related to study drug, restart study drug at next lower dose; monitor as clinically indicated.

Other toxicities	
Any Grade 1 or Grade 2 toxicity	Continue study drug treatment and treat the toxicity; monitor as clinically indicated
Any Grade 3 toxicity, if clinically significant and not manageable by supportive care	
Step 1: interrupt study drug up to 2 weeks (14 days) until the toxicity has resolved to \leq Grade 1 except by approval of the medical monitor
 
Step 2: If assessed as related to study drug, restart study drug at next lower dose; monitor as clinically indicated.

Any recurrent Grade 3 toxicity after 2 dose reductions	Discontinue study drug administration.
Any Grade 4 toxicity	Discontinue study drug administration.

4.3.7 Management of Hyperphosphatemia and Serous Retinal Detachment

Table: Recommended Approach for Hyperphosphatemia management:

Serum Phosphate Level	Supportive Care	Guidance for Interruption/Discontinuation of INCB054828	Guidance for Restarting INCB054828
> 5.5 mg/dL and ≤ 7 mg/dL	Initiate a low-phosphate diet.	No action.	Not applicable.
> 7 mg/dL and ≤ 10 mg/dL	Initiate/continue a low-phosphate diet and initiate phosphate-binding therapy once serum phosphate level is > 7 mg/dL. Monitor serum phosphate at least twice a week and adjust the dose of binders as needed; continue to monitor serum phosphate at least twice a week until return to normal range.	If serum phosphate level continues to be > 7 mg/dL and ≤ 10 mg/dL with concomitant phosphate-binding therapy for 2 weeks, or if there is recurrence of serum phosphate level in this range, interrupt INCB054828 for up to 2 weeks (not including the planned dose interruption per treatment cycle).	Restart at the same dose when serum phosphate is < 7 mg/dL. If serum phosphate level recurs at > 7 mg/dL, restart INCB054828 with dose reduction.
> 10 mg/dL	Continue to maintain a low-phosphate diet, adjust phosphate-binding therapy, and start/continue phosphaturic agent. Continue to monitor serum phosphate at least twice a week until return to normal range.	If serum phosphate level is > 10 mg/dL for 1 week following phosphate-binding therapy and low phosphate diet, interrupt INCB054828. If there is recurrence of serum phosphate level in this range following 2 dose reductions, permanently discontinue INCB054828.	Restart INCB054828 at reduced dose with phosphate binders when serum phosphate is < 7 mg/dL.

Table: Recommended Approach for Serous Retinal Detachment*

RETINAL DETACHMENT	ACTION TAKEN
Mild and moderate	Monitor with ophthalmology examination
Mild and moderate with Worsening Vision	Interrupt study drug administration until the toxicity has resolved or vision improved
Worsening	Interrupt study drug administration until the toxicity has resolved to mild/moderate
Severe (Grade 3)	Interrupt study drug administration until the toxicity has resolved to mild/moderate

*participants should be monitored for signs and symptoms of serous retinal detachment, and the retina should be assessed with optical coherence tomography

4.3.8 Criteria for permanent discontinuation of study drug

The occurrence of unacceptable toxicity not caused by the underlying malignancy will be presumed to be related to study drug treatment and will require that the study drug be permanently discontinued. Unacceptable toxicity is defined as follows:

- Occurrence of an AE that is related to treatment with the study drug that, in the judgment of the investigator or the sponsor's medical monitor, compromises the subject's ability to continue study-specific procedures or is considered to be not in the subject's best interest.
- An AE requiring more than 2 dose reductions, if below the minimal biologically active dose of

Pemigatinib.

- Persistent AE requiring a interruption of therapy for more than 21 days unless a greater period of interruption has been approved by the sponsor.
- Increase in QT/QTc to > 500 milliseconds or to > 60 milliseconds over baseline.

4.4 During Treatment- & Follow-Up Procedures

4.4.1 Concomitant Medication

Concomitant medication has to be documented during the treatment phase. In case of existing possible treatment related adverse events after the treatment phase concomitant medication documentation has to be continued. During the study, other treatments or the administration of other drugs for the treatment of MIBC are not permitted. Any other non-experimental drug(s) in treatment for other indications are permitted if they are not prohibited (as indicated below), provided they are recorded in the eCRF.

Restricted medications:

The use of mild or moderate CYP3A4 inhibitors or inducers should involve careful monitoring. The pH level of stomach acid impacts the absorption of Pemigatinib. As a result, limited use of proton pump inhibitors or antacids while on study is recommended. Use of calcium-based phosphate-binding medications while on study is cautioned due to a concern for soft tissue mineralization.

Close clinical surveillance is recommended when pemigatinib is administered with medicinal products containing P-gp or OCT2 / MATE1 substrates.

Prohibited medications:

The following medications and measures are prohibited:

- The concomitant administration of potent CYP3A4 inhibitors and inducers (Appendix 5) is prohibited. Based on the low overall bioavailability of topical ketoconazole, there are no restrictions in its use.
- Any concomitant use of a selective FGFR inhibitor is prohibited.
- Investigational study drug for any indication is prohibited.
- Use of any anticancer medications other than the study medication from 21 days before Day 1 is prohibited.

4.4.2 Other During Treatment Examinations

The investigator or qualified designee will obtain results of WHO performance status, ECG, ophthalmological-, laboratory- and radiological tests as described in the flowchart (Appendix 6).

4.4.3 Relapse or Progression

All types of relapse will be included i.e. local, regional and distant metastasis as well as second primary tumor of the upper urinary tract. In addition, all deaths occurring without prior documentation of tumor relapse will be considered as an event. Any new primary cancer will not be considered as relapse and should be reported as SAE. All relapses must be documented by radiological evidence or biopsy, as determined by the investigator. Suspicion of relapse based on physical examination findings or laboratory signs must be confirmed by radiological examination

and/or biopsy. Equivocal findings on standard radiological imaging should be confirmed by repeated examinations or cytology/histology or other imaging techniques. The date of relapse or progression as indicated by the date of radiology or biopsy as confirmed by the investigator, will be used as the timepoint of relapse or progression. At disease relapse or progression, a biopsy and subsequent genomic sequencing at the sponsors central laboratory is recommended after written informed consent of the patient.

4.4.4 Subsequent Anti-Cancer Therapy Status

The investigator or qualified designee will review all new anti-neoplastic therapy initiated after the last dose of trial treatment. If a participant initiates a new anti-cancer therapy within 30 days after the last dose of trial treatment, the 30 day Safety Follow-up visit must occur before the first dose of the new therapy. Once new anti-cancer therapy has been initiated the participant will move into survival follow-up.

4.4.5 Adverse Events

The investigator or qualified designee will report all adverse events and serious adverse events as indicated in chapter 6.

4.5 Pregnancy

Patients or partners of patients who become pregnant during the study treatment phase must not receive additional doses of study treatment but may continue other study procedures at the discretion of the investigator.

The investigator, or his/her designee, will collect pregnancy information on any patient or partner of the patient who becomes pregnant while participating in this study i.e. from signature of informed consent till 3 months after the last study treatment. The investigator, or his/her designee, will record pregnancy information on the Pregnancy Report Form and submit it to the Sponsor within 24 hours of learning of a patient's or partner of patient's pregnancy. The pregnancy will be followed to determine the outcome. At the end of the pregnancy, whether that be full-term or prematurely, information on the status of the mother and child will be forwarded to the Sponsor. Generally, follow-up will be no longer than 6 to 8 weeks following the estimated delivery date.

While pregnancy itself is not considered an AE or SAE, any pregnancy complication or elective termination of a pregnancy for medical reasons will be recorded and followed as an AE or a SAE, as described in Section 6.1 and 6.2.

A spontaneous abortion is always considered to be a SAE and will be reported as described in Section 6.2. Furthermore, any SAE occurring as a result of a post-study pregnancy AND considered reasonably related in time to the investigational product by the investigator, will be reported to the Sponsor as described in Section 6.3. While the investigator is not obligated to actively seek this information from former study participants, he/she may learn of a pregnancy through spontaneous reporting.

4.6 Premature Termination of the Study

For reasonable cause, the Sponsor, may terminate this study provided a written notice is submitted at a reasonable time in advance of intended termination.

5. PATIENT SELECTION & WITHDRAWAL CRITERIA

5.1 Study Population

A total of 56 patients with FGFR alterations as assessed by a centralized Foundation Medicine test (Foundation One) will be eligible to start Pemigatinib after providing their informed consent if they meet all of the following inclusion criteria.

5.2 Inclusion Criteria

1. Men and women, aged 18 years or older with histological evidence of pT3-4 and/or pN1-3 urothelial cancer (UC) of the urinary bladder or upper urinary tract after radical cystectomy / radical nephroureterectomy. Patients with mixed histologies are required to have a dominant (i.e. at least 50%) urothelial cell carcinoma pattern.
2. Previous administration of at least 2-3 cycles of neoadjuvant cisplatin-based chemotherapy OR, if neoadjuvant chemotherapy was not administered, ineligibility to receive cisplatin-based adjuvant chemotherapy based on Galsky's criteria, that include at least one of the following: (1) WHO performance status ≥ 2 and/or (2) creatinine-clearance < 60 ml/min and/or (3) CTCAE Gr ≥ 2 hearing loss and/or (4) CTCAE Gr ≥ 2 neuropathy [23].
3. Evidence of FGFR3 alterations (mutations or gene fusions as specified in protocol) as assessed by a centralized Foundation Medicine test (Foundation One CDx assay).

A list of the allowed FGFR alterations is provided below.

GENE	ALTERATION
FGFR3	R248C
FGFR3	S249C
FGFR3	G370C
FGFR3	S371C
FGFR3	Y373C
FGFR3	G380R
FGFR3	G380E
FGFR3	A391E
FGFR3	R399C
FGFR3	S433C
FGFR3	D641N
FGFR3	K650M
FGFR3	K650E
FGFR3	K650Q
FGFR3	K650T
FGFR3	K650N
FGFR3	Novel FGFR3 fusion (with partner specified)
FGFR3	FGFR3-BAIAP2L1
FGFR3	FGFR3-IGH
FGFR3	FGFR3-TACC3
FGFR3	FGFR3-WHSC1

4. Recovered with no evidence of disease confirmed by radiological images, prior to start of adjuvant therapy within 13 weeks after radical surgery.
5. WHO performance status of 0, 1 or 2.

6. Willingness to avoid pregnancy or fathering children. If the patient is male, he must use a condom during sexual intercourse during the treatment period and 240 days thereafter (120 days to eliminate study treatment and 120 days spermatogenesis cycle) **plus** partner use of a contraceptive method with a failure rate of <1% per year (See Appendix 1). If the patient is female, and of childbearing potential, she must practice adequate contraception (Appendix 1) for 30 days prior to administration of study treatment, have a negative pregnancy test and continue such precautions during the study treatment period and for 150 days after the last study treatment (120 days to eliminate study treatment and 30 days menstruation cycle) (See Appendix 1 for standards of adequate contraceptive methods).
7. Written informed consent for screening of tumor tissue and if evidence of FGFR alterations written informed consent for the start of the complete study.

5.3 Exclusion Criteria

Patients with any of the following exclusion criteria will NOT be eligible for the study:

1. Any previous receipt of a selective FGFR inhibitor.
2. Presence of primary CIS only.
3. Presence of another malignancy in the 3 years before enrolment except for basal cell carcinoma or squamous cell carcinoma of the skin, cis of cervix, localised prostate cancer in active surveillance or other non invasive or other indolent malignancy that has undergone potentially curative therapy.
4. Presence of pregnancy or lactation or not willing to avoid pregnancy or fathering children.
5. Distant metastases (M1 disease) or presence of radiological evidence of disease at baseline.
6. Treatment with other investigational drugs, receipt of anticancer medications (except for neoadjuvant cisplatin-based chemotherapy, see second inclusion criterion) or radiotherapy of the bladder or upper urinary tract prior to- or after radical surgery.
7. Use of any potent CYP3A4 inhibitors or inducers within 14 days or 5 half lives (whichever is longer) before the first dose of study Tx.
8. Abnormal laboratory parameters:
 - i. Total bilirubin $\geq 1.5 \times$ upper limit of normal (ULN; $\geq 2.5 \times$ ULN if Gilbert syndrome).
 - ii. AST and/or ALT $> 2.5 \times$ ULN
 - iii. Creatinine clearance ≤ 30 mL/min based on Cockcroft-Gault.
 - iv. Serum phosphate $>$ institutional ULN.
 - v. Serum calcium outside of the institutional normal range or serum albumin-corrected calcium outside of the institutional normal range when serum albumin is outside of the institutional normal range.
9. History of human immunodeficiency virus infection or active tuberculosis infection.
10. Diagnosis of immunodeficiency or receiving chronic systemic steroid therapy (exceeding > 10 mg daily of prednison equivalent; inhalation steroids are permitted).
11. Evidence of hepatitis B virus or hepatitis C virus active infection or risk of reactivation.
12. Severe hepatic impairment .
13. Known prior severe hypersensitivity to investigational product or its excipients.

14. History of clinically significant or uncontrolled cardiac disease, including unstable angina, acute myocardial infarction within 6 months from enrollment, NYHA Class III or IV (Appendix 4).
15. Current evidence of corneal disorder/keratopathy (including but not limited to bullous/band keratopathy, corneal abrasion, inflammation/ulceration, keratoconjunctivitis, etc) or retinal disorder (including but not limited to, central serous retinopathy, macular/retinal degeneration, diabetic retino-pathy, retinal detachment, etc) as confirmed by ophthalmologic examination.
16. Any condition that would, in the investigator's judgment, interfere with full participation in the study, including administration of study drug and attending the required study visits.

5.4 Patient Withdrawal and Early Dropouts (off study)

In the patient informed consent form the patients will be informed that they have the right to withdraw from the study at any time without affecting their subsequent care and may be withdrawn at the investigator's discretion at any time. In the event that the patient drops out, the investigator will, if possible, indicate the reason for withdrawal. Reasonable effort will be made to contact any patient lost to follow up during the course of the study in order to complete assessments and retrieve any outstanding data. Patients withdrawn from the trial will not be replaced.

Off study criteria:

- When the investigator considers it in the best interest of the patient that he/she will be withdrawn
- Patient or legal representative request withdrawal of informed consent
- Lost to follow up or administrative reasons
- Non-compliance with study treatment or procedure requirements.
- Study termination by ethical- or health authorities or the Sponsor.
- Others, only applicable after consultation with the sponsors study monitor.

Participants who discontinue study treatment prior to completion of the treatment period should be encouraged to continue to be followed for all remaining study visits.

When a participant discontinues/withdraws from participation in the trial, if possible, all applicable activities scheduled for the final study visit should be performed at the time of discontinuation. Any adverse events which are present at the time of discontinuation/withdrawal should be followed in accordance with the safety requirements outlined in chapter 6 - Adverse Events.

If the patient discontinues study treatment and actively withdraws consent for collection of follow-up data (safety follow-up or disease assessment), then no additional data collection should occur; however, patients will have the option of withdrawing consent for study treatment but continuing in the follow-up period of the study for safety/efficacy assessments.

Notes:

- Patients who experience unacceptable study drug related adverse events should stop treatment with the study drug. These patients continue follow up for disease status and survival.

- Patients who develop a relapse or metastases of disease stop study drug treatment and they are asked to consent with biopsy and subsequent genomic sequencing after relapse or metastases, whereafter follow up for survival only is continued.
- Patients who become pregnant should stop study drug treatment and should be followed for the outcome of pregnancy and survival.

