4.1.3 End of Treatment

When the subject permanently discontinues study drug, the end of treatment (EOT) visit should be conducted. If the EOT visit coincides with a regular study visit, the EOT evaluations will supersede those of that scheduled visit, and the data should be entered in the EOT visit in the eCRF. The subject should be encouraged to return for the follow-up visit.

4.1.4 Safety Follow-up:

The safety follow-up period is the interval between the EOT visit and the scheduled follow-up visit, which should occur 30 to 35 days after the EOT visit (or after the last dose of study drug if the EOT visit was not performed). Adverse events and SAEs must be reported until at least 30 days after the last dose of study drug; or until toxicities resolve, return to baseline, or are deemed irreversible; death; or initiation of a new anticancer treatment, whichever occurs first. Reasonable efforts should be made to have the subject return for the follow-up visit and report any AEs that may occur during this period.

If a subject is scheduled to begin a new anticancer therapy before the end of the 30-day safety follow-up period, the safety follow-up visit should be performed before new anticancer therapy is started. Once new anticancer therapy has been initiated, the subject will move into the survival follow-up period.

4.1.5 Disease Status Follow-up:

Subjects who discontinue study treatment for a reason other than disease relapse or progression will move into the disease status follow-up period and should be assessed every 12 weeks by radiologic

imaging to monitor disease status. Every effort should be made to collect information regarding disease status until:

- The start of new antineoplastic therapy.
- Disease relapse or progression.
- Death.
- The end of the study.

At disease relapse or progression, a biopsy and subsequent genomic sequencing at the sponsors central laboratory is recommended after written informed consent of the patient.

4.1.6 Survival Follow-up:

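### Section 5.4 takes patients off study for treatment non-compliance while 4.1.5 keeps them in imaging follow-up, so some who have not withdrawn consent can drop out of the 2-year RFS rate

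*Combined protocol and SAP*

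**What the plan says.** Section 5.4 deals with withdrawal and early dropout, and its heading equates these with being off study. Its list of off-study criteria includes "Non-compliance with study treatment or procedure requirements" and "When the investigator considers it in the best interest of the patient that he/she will be withdrawn". These stand beside withdrawal of consent, loss to follow-up or administrative reasons, study termination, and other reasons agreed with the sponsor's monitor. The same section adds: "Patients withdrawn from the trial will not be replaced".

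Section 4.1.5 says: "Subjects who discontinue study treatment for a reason other than disease relapse or progression will move into the disease status follow-up period", with imaging every 12 weeks. It continues, "Every effort should be made to collect information regarding disease status until", and gives four end points: new antineoplastic therapy, relapse or progression, death, and end of study. Non-compliance is not among them.

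Other sentences of 5.4 point the same way as 4.1.5. Patients who stop treatment early "should be encouraged to continue to be followed for all remaining study visits". On consent, "patients will have the option of withdrawing consent for study treatment but continuing in the follow-up period of the study". After a stop for unacceptable drug-related toxicity, "These patients continue follow up for disease status and survival".

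Three further sections matter. Section 4.3.4 measures compliance by tablet count and sets no level below which a patient is non-compliant. Section 7.1 leaves patients who withdraw before 2 years out of the 2-year RFS rate, expects about 15% to be withdrawn, and enrols 56 to obtain 50. Section 7.2 names the ITT population for the primary analysis.

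**The concern.** The off-study list mixes two kinds of event: those that end observation, such as withdrawal of consent or loss to follow-up, and one that describes how the patient takes the drug. Under 5.4 the second kind can also end observation, although the patient has not asked to leave and 4.1.5 would keep the scans going.

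The label is undefined and applied by the site in an open-label trial. Poor tolerance can lead to missed tablets: section 4.3.5 reports stomatitis in 48% and diarrhoea in 39% of patients on continuous dosing. Similar patients could then be kept or lost depending on the reason recorded. With a single arm, no control group undergoes the same selection. A relapse status that was never collected also cannot be restored by a later choice of analysis population or censoring rule.

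**Working it through.** **1. The two rules applied to one patient.** Take a patient who stops taking tablets, has no relapse and has not withdrawn consent.

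- Under 4.1.5 the patient has stopped treatment for a reason other than relapse or progression, so 12-weekly imaging continues until one of the four listed end points.
- Under the 5.4 list the patient meets an off-study criterion, and 5.4 treats off study as withdrawal.
- Under 7.1 a patient withdrawn before 2 years is not counted in the 2-year RFS rate, and 5.4 allows no replacement.

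No sentence says which rule prevails. The conflict concerns non-compliance with treatment. Non-compliance with procedures means missed visits or scans, where data are lost whatever the label.

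**2. The plan's own design.** Inputs from 7.1: 30% versus 45% relapse-free at 2 years, one-sided alpha 0.10, power 0.80, exact single-stage design. The smallest n with a cut-off r such that P(X ≥ r | 0.30) ≤ 0.10 and P(X ≥ r | 0.45) ≥ 0.80 is n = 50 with r = 20 relapse-free. Exact alpha is 0.0848 and power 0.8026, so the stated 50 is reproduced. (Section 7.1 words its cut-off of 20 in terms of relapses. That is a separate matter; the 20 relapse-free required by the exact design is used here.)

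**3. Room for loss.** (56 − 50)/56 = 10.7%, against the roughly 15% expected. At 15%, 56 × 0.85 = 47.6 remain. With n = 47 and r = 19, power is 0.781; with n = 48 and r = 20, it is 0.728. If all 56 are followed, r = 22 gives alpha 0.087 and power 0.840. The 15% covers withdrawals of every kind, so only part of this loss could come from non-compliance.

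**4. Effect on type I error.** The documents give neither a non-compliance rate nor an outcome for such patients, so both are assumed over a range. Let the true rate in all enrolled patients be p = 0.30, the fraction removed d, and the relapse-free rate of those removed q. The rate among those analysed is

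p_obs = (p − d·q)/(1 − d).

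For d = 0.10, 56 × 0.90 = 50.4, so n = 50 and r = 20:

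- q = 0: p_obs = 0.30/0.90 = 0.333
- q = 0.15: p_obs = 0.285/0.90 = 0.317
- q = 0.30: p_obs = 0.27/0.90 = 0.300
- q = 0.45: p_obs = 0.255/0.90 = 0.283

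Type I error is P(X ≥ r | n, p_obs):

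| Removed | n, r | q = 0 | q = 0.15 | q = 0.30 | q = 0.45 |
|---|---|---|---|---|---|
| 5% | 53, 21 | 0.134 | 0.108 | 0.086 | 0.068 |
| 10% | 50, 20 | 0.196 | 0.133 | 0.085 | 0.050 |
| 15% | 48, 20 | 0.218 | 0.120 | 0.057 | 0.023 |

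The column q = 0.30 is the case without bias. To its left the error rises above the planned 0.10; to its right the test becomes conservative.

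**The case against.** The strongest reply is that the documents, taken together, lean towards keeping these patients. Section 4.1.5 asks for every effort to obtain disease status. Section 5.4 encourages those who stop treatment to stay, lets patients leave treatment only, and keeps toxicity stops in follow-up. It ties an end to data collection only to active withdrawal of consent for follow-up. Missed doses are simply recorded under 4.1.2, and toxicity has its own route in 4.3.6 and 4.3.8. A loss therefore requires a site to choose the off-study criterion over these texts.

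This stands, and it limits the point. A reader might infer that the endpoint is lost for everyone who merely stops the drug, or that relapse and survival are never collected for them. The documents do not support either reading: the data may not be collected, and only for patients labelled non-compliant. Some information also survives, because final-visit activities are done where possible and RFS is shown by Kaplan-Meier under 7.4.2.

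A reader might also take an assumed loss of, say, 8 of 56, read it as a 14-point best-to-worst-case range, and set that against the 15-point design effect. That comparison is not sound. It assumes that all lost patients relapsed or that none did, and 8 would use up every expected withdrawal.

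The objection does not remove the conflict. Encouragement to stay does not override an explicit criterion for going off study, treatment-only withdrawal depends on the patient's choice, and the toxicity note covers only unacceptable drug-related events. Kaplan-Meier estimation uses time up to exit but relies on exit being unrelated to prognosis.

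**Conclusion.** The point holds as a conflict between rules that can reach the primary endpoint. A patient who has not withdrawn consent, but is labelled non-compliant with treatment, is off study under 5.4 and in follow-up under 4.1.5. If the site follows 5.4, section 7.1 drops the patient from the 2-year rate, and naming the ITT population does not bring the missing status back.

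The size is not known from the documents. Under the assumptions in the table, removing 10% moves type I error anywhere from 0.050 to 0.196, against 0.085 without bias. That result rests on the 7.1 exclusion being applied, on a true rate of 30%, and on the assumed outcomes of those removed. A reader might infer that the bias favours the drug; nothing in the documents fixes its direction. The matter deserves correction because data not collected during the trial may not be recoverable later.

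**What to change.** Reconcile 5.4 with 4.1.5 and 4.1.6 by separating end of treatment from end of study:

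- State that non-compliance with study treatment does not by itself end disease-status or survival follow-up. Follow-up then ends early only if the patient withdraws consent to it, is lost, or the study ends. The existing 4.1.5 end points for imaging stay as they are.
- Record end of treatment and study exit as separate items, each with its own date and reason.
- Keep the investigator's discretion to withdraw a patient, with survival status still sought where consent allows.

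This concerns data collection only and proposes no rule for stopping treatment. The conflict between the 7.1 exclusion and ITT in 7.2 needs its own resolution.

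The cost is a change of wording, the separate recording, and a little extra follow-up effort. The 12-weekly scans and survival contacts are already scheduled in 4.1.5, 4.1.6 and Appendix 6. Some non-compliant patients will still miss visits, so the loss will be reduced rather than removed.
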